**Panel 6: Adjacent IGA-CHE scores combined in case of missing predictors in observed data**

IGA-CHE score(s) missing in imputation model	IGA-CHE scores combined
0	(0,1) scores combined to 1
1	(0,1) scores combined to 1
2	(2,3) scores combined to 3
3	(2,3) scores combined to 3
4	(3,4) scores combined to 3

**5.1.1.1.2 Multiple imputation based on Bernoulli distribution**

For imputation of missing IGA-CHE scores using the Bernoulli distribution the following will be applied: In both treatment groups missing data will be imputed from a Bernoulli distribution with parameter  $p = 0.1$ . A MI procedure (100 iterations) will be used.

**5.1.1.2 Worst observation carried forward**

For the analyses of continuous data WOCF is used to impute missing data and data treated as missing. When WOCF is used, missing values are imputed with the subject's worst-case non-missing value (including the baseline value) and thereby represents no treatment effect.

**5.2 Extent of exposure**

The duration of exposure to treatment will be calculated as the number of days from date of first application of IMP to the date of last application of IMP, both days included.

Exposure to IMP will be presented for the SAF as days of exposure per treatment group. In addition, patient years of exposure and patient years of observation are presented per treatment group. Patient years of exposure will be calculated as the number of days from date of first application of IMP to the date of last application of IMP (both days included) divided by 365.25. Patient years of observation is calculated as number of days from date of randomisation to date of end of trial divided by 365.25.

THIS DOCUMENT CONTAINS CONFIDENTIAL INFORMATION AND MUST NOT BE COPIED OR MADE AVAILABLE TO ANY THIRD PARTY WITHOUT THE PRIOR WRITTEN CONSENT OF THE LEO PHARMA GROUP

In case subjects come in after end of trial (the safety follow-up visit) to e.g., hand in slates or update information on adverse events the time between end of trial and this last contact will not be added to the years of observation.

### 5.3 Intercurrent events

The following intercurrent events are considered to affect the interpretation of the estimated treatment effects.

- **Initiation of rescue treatment:** This IE occurs when a subject initiates rescue treatment. This IE can occur at the discretion of the investigator. If rescue treatment is initiated, the subject must stop treatment with IMP immediately and will not be allowed to restart treatment with IMP. The date of the IE is the start date of initiation of the rescue treatment. For further information about the definition of rescue treatment see Appendix [7.3.5](#).
- **Permanent discontinuation of IMP:** This IE occurs when a subject permanently discontinues IMP. This IE can occur at the subject's own initiative, at the subject's parent's/guardian's initiative, at the discretion of the investigator or the sponsor, or if the subject is lost to follow-up. The date of the IE is the date following the date of last application of IMP.

Journeys of 4 subjects from randomization to primary endpoint visit are illustrated in [Panel 7](#).

### Panel 7: Subject journeys with intercurrent events

**Notes:** Subject 1 completes the treatment period, subject 2 permanently discontinues IMP, subject 3 discontinues IMP and then initiates rescue treatment, while subject 4 initiates rescue treatment and subsequently discontinues IMP.

If a subject experiences more than one IE, the first IE occurring will be used when addressing IEs in the statistical analyses. If both types of IEs occur on the same day, handling of observed and missing data will be done in accordance with [Panel 8](#), as methods described are identical for the two IEs. The number of IEs and type of IEs will be summarized by treatment group and visit interval. For further information about how permanent discontinuation of IMP and rescue treatment data will be summarized see Appendix [7.3.2](#) and [7.3.5](#), respectively.

#### 5.3.1 Handling of observed and missing data according to intercurrent events

An overview of how observed and missing data will be handled according to the IEs for all analyses for the two estimands are presented in [Panel 8](#).

THIS DOCUMENT CONTAINS CONFIDENTIAL INFORMATION AND MUST NOT BE COPIED OR MADE AVAILABLE TO ANY THIRD PARTY WITHOUT THE PRIOR WRITTEN CONSENT OF THE LEO PHARMA GROUP

**Panel 8: Handling of observed and missing data in the analyses according to the intercurrent events**

		Estimand strategy for binary endpoints					Estimand strategy for continuous endpoints
		Composite strategy			Treatment policy strategy		Composite strategy
Intercurrent event	Data observed or missing	Bayes: • Primary endpoint primary analysis • Key secondary endpoints  analyses	Frequentist: • Primary endpoint primary analysis • Primary endpoint supplementary analysis using historical data • Primary endpoint additional analysis • Key secondary endpoints  analyses • Secondary endpoints  analyses • Exploratory endpoints  analyses	Frequentist: • Primary endpoint sensitivity analysis • Sensitivity analysis of primary endpoint additional analysis	Frequentist: • Primary endpoint analysis • Primary endpoint additional analysis	Frequentist: • Primary endpoint sensitivity analysis • Sensitivity analysis of primary endpoint additional analysis	Frequentist: • Secondary endpoints  analyses • Exploratory endpoints  analyses
Initiation of rescue treatment	Observed	Non-response		Non-response	Value will be used as observed	Value will be used as observed	WOCF (including baseline value)
	Missing	Non-response		Non-response	MI (MAR)	Non-response	WOCF (including baseline value)
Permanent discontinuation of IMP	Observed	Non-response		Non-response	Value will be used as observed	Value will be used as observed	WOCF (including baseline value)
	Missing	Non-response		Non-response	MI (MAR)	Non-response	WOCF (including baseline value)
No intercurrent events	Observed	Value will be used as observed		Value will be used as observed	Value will be used as observed	Value will be used as observed	Value will be used as observed

THIS DOCUMENT CONTAINS CONFIDENTIAL INFORMATION AND MUST NOT BE COPIED OR MADE AVAILABLE TO ANY THIRD PARTY WITHOUT THE PRIOR WRITTEN CONSENT OF THE LEO PHARMA GROUP

	Missing	Non-response	MI using Bernoulli distribution	MI (MAR)	Non-response	WOCF (including baseline value)
--	---------	--------------	---------------------------------	----------	--------------	---------------------------------

## 1. Key secondary endpoints:

- HECSI-90 at week 16.
- Reduction of HESD itch score (weekly average) of  $\geq 4$  points from baseline at Week 16 (among subjects with a baseline HESD itch score (weekly average)  $\geq 4$  points).
- Reduction of HESD pain score (weekly average) of  $\geq 4$  points from baseline at Week 16 (among subjects with a baseline HESD pain score (weekly average)  $\geq 4$  points).
- Reduction of HESD score (weekly average) of  $\geq 4$  points from baseline at Week 16 (among subjects with a baseline HESD score (weekly average)  $\geq 4$  points).

## 2. Secondary endpoints:

- IGA CHE TS at Weeks 2, 4, 8, and 12.
- Change in cDLQI score from baseline to Week 16.

## 3. Exploratory endpoints:

- HECSI-75 at Weeks 4, 8, and 16.
- HECSI-90 at Weeks 4 and 8.
- Percentage change in HECSI score from baseline to Weeks 4, 8, and 16.
- Reduction of HESD itch score (weekly average) of  $\geq 3$  points from baseline at Weeks 2, 4, 8 and 16 (among subjects with a baseline HESD itch score (weekly average)  $\geq 3$  points).
- Reduction of HESD itch score (weekly average) of  $\geq 4$  points from baseline at Weeks 2, 4, and 8 (among subjects with a baseline HESD itch score (weekly average)  $\geq 4$  points).
- Change in HESD itch score (weekly average) from baseline to Weeks 2, 4, 8, and 16.
- Reduction of HESD pain score (weekly average) of  $\geq 3$  points from baseline at Weeks 2, 4, 8 and 16 (among subjects with a baseline HESD pain score (weekly average)  $\geq 3$  points).
- Reduction of HESD pain score (weekly average) of  $\geq 4$  points from baseline at Weeks 2, 4, and 8 (among subjects with a baseline HESD pain score (weekly average)  $\geq 4$  points).
- Change in HESD pain score (weekly average) from baseline to Weeks 2, 4, 8, and 16.
- Reduction of HESD score (weekly average) of  $\geq 3$  points from baseline at Weeks 2, 4, 8, and 16 (among subjects with a baseline HESD score (weekly average)  $\geq 3$  points).
- Reduction of HESD score (weekly average) of  $\geq 4$  points from baseline at Weeks 2, 4, and 8 (among subjects with a baseline HESD score (weekly average)  $\geq 4$  points).
- Change in HESD score (weekly average) from baseline to Weeks 2, 4, 8, and 16;
- Change in cDLQI score from baseline to Week 4.

**Abbreviations:** IMP = investigational medicinal product; MAR = missing at random; MI = multiple imputation; WOCF = worst observation carried forward.

THIS DOCUMENT CONTAINS CONFIDENTIAL INFORMATION AND MUST NOT BE COPIED OR MADE AVAILABLE TO ANY THIRD PARTY WITHOUT THE PRIOR WRITTEN CONSENT OF THE LEO PHARMA GROUP

## 5.4 Estimand overview

The primary endpoint for LP0133-1426 is IGA-CHE TS at Week 16, and the primary estimand uses the composite strategy when handling intercurrent events. With a composite strategy, the occurrence of an IE is a component of the endpoint.

For the analyses based on the Bayesian approach, only the primary estimand using the composite strategy will be used.

For the analyses based on the Frequentist approach, both the primary estimand (using the composite strategy) and the supplementary estimand (using the treatment policy strategy) will be considered for the primary endpoint. For the other endpoints the primary estimand will be the only one used.

The supplementary estimand uses a treatment policy strategy which attempts to quantify the effect of the randomised treatment, ignoring the occurrence of IEs. Data collected for the endpoint of interest are used regardless of whether an IE occurred.

## 5.5 Primary estimand

The primary estimand defined for the binary and continuous endpoints uses the composite strategy.

### 5.5.1 Primary estimand for binary endpoints: composite strategy, used for both the Bayesian approach and the Frequentist approach

The primary estimand “Composite strategy” evaluates the treatment effect in adolescents 12-17 years of age with moderate to severe CHE as the risk difference for achieving a response, without initiation of rescue treatment or permanent discontinuation of IMP.

For subjects who received rescue treatment or who have permanently discontinued IMP prior to the endpoint of interest, observed data after the IEs will be considered non-response, reflecting an assumption that initiation of rescue treatment and permanent discontinuation of IMP indicate failure of the randomised treatment.

For example, the primary composite endpoint of IGA-CHE TS at Week 16 without initiation of rescue treatment or permanent discontinuation of IMP can take the values:

- ‘1’ (response), if the subject achieves IGA-CHE TS at Week 16 and has neither initiated rescue treatment nor permanently discontinued IMP prior to Week 16.

THIS DOCUMENT CONTAINS CONFIDENTIAL INFORMATION AND MUST NOT BE COPIED OR MADE AVAILABLE TO ANY THIRD PARTY WITHOUT THE PRIOR WRITTEN CONSENT OF THE LEO PHARMA GROUP

- '0' (non-response), if the subject has not achieved IGA-CHE TS at Week 16 or has initiated rescue treatment or permanently discontinued IMP prior to Week 16.

Missing data for subjects who do not experience an IE prior to the visit for the endpoint of interest will be imputed as non-response, except in the sensitivity analysis where these are imputed from a Bernoulli distribution. Similarly, missing data at the endpoint of interest for subjects who do experience an IE prior to this visit will be imputed as non-response.

#### 5.5.1.1 Definition of binary endpoints

The primary endpoint for LP0133-1426 is the binary endpoint "IGA CHE TS at Week 16 (IGA CHE TS refers to a score of 0 [clear] or 1 [almost clear] with a  $\geq 2$  step improvement from baseline)".

The remaining binary endpoints (key secondary, secondary, and exploratory) are:

- HECSI 90 at Week 16.
- Reduction of HESD itch score (weekly average) of  $\geq 4$  points from baseline at Week 16 (Among subjects with a baseline HESD itch score (weekly average)  $\geq 4$  points.).
- Reduction of HESD pain score (weekly average) of  $\geq 4$  points from baseline at Week 16 (Among subjects with a baseline HESD pain score (weekly average)  $\geq 4$  points.).
- Reduction of HESD score (weekly average) of  $\geq 4$  points from baseline at Week 16 (Among subjects with a baseline HESD score (weekly average)  $\geq 4$  points.).
- IGA-CHE TS at Weeks 2, 4, 8, and 12.
- HECSI-90 at Weeks 4, 8 and 16.
- HECSI-75 at Weeks 4, 8, and 16.
- Reduction of HESD itch score (weekly average) of  $\geq 4$  points from baseline at Weeks 2, 4, 8 and 16 (Among subjects with a baseline HESD itch score (weekly average)  $\geq 4$  points.).
- Reduction of HESD itch score (weekly average) of  $\geq 3$  points from baseline at Weeks 2, 4, 8, and 16 (Among subjects with a baseline HESD itch score (weekly average)  $\geq 3$  points.).
- Reduction of HESD pain score (weekly average) of  $\geq 4$  points from baseline at Weeks 2, 4, 8 and 16 (Among subjects with a baseline HESD pain score (weekly average)  $\geq 4$  points.).
- Reduction of HESD pain score (weekly average) of  $\geq 3$  points from baseline at Weeks 2, 4, 8, and 16 (Among subjects with a baseline HESD pain score (weekly average)  $\geq 3$  points.).

THIS DOCUMENT CONTAINS CONFIDENTIAL INFORMATION AND MUST NOT BE COPIED OR MADE AVAILABLE TO ANY THIRD PARTY WITHOUT THE PRIOR WRITTEN CONSENT OF THE LEO PHARMA GROUP

- Reduction of HESD score (weekly average) of  $\geq 4$  points from baseline at Weeks 2, 4, 8 and 16 (Among subjects with a baseline HESD score (weekly average)  $\geq 4$  points).
- Reduction of HESD score (weekly average) of  $\geq 3$  points from baseline at Weeks 2, 4, 8, and 16 (Among subjects with a baseline HESD score (weekly average)  $\geq 3$  points.).

#### **5.5.1.2 Primary endpoint analysis using the primary estimand, Frequentist approach**

The primary endpoint will be analysed as follows: Let the treatment effect be defined as the risk difference  $\mu$  = (delgocitinib cream 20 mg/g minus cream vehicle), then the hypothesis to be tested is:

- $H_0: \mu \leq 0$  against  $H_a: \mu > 0$ .

The hypothesis will be tested for delgocitinib cream 20 mg/g vs. cream vehicle based on the primary analysis for the primary estimand.

Missing data for subjects who do not attend the visit for the endpoint of interest and do not experience an IE prior to this visit will be imputed as non-response.

The risk difference between the 2 treatment groups will be based on a logistic regression model including treatment group and baseline IGA-CHE score as factors. The logistic regression model will be used to estimate the risk difference and associated 95% confidence interval based on the standardised estimator presented in Ge M et al. (2) and the variance estimator presented in Bartlett JW (3).

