### 14.1 Sample size

92 subjects will be randomised 3:1 to delgocitinib cream 20 mg/g or cream vehicle.

Based on response rates from the phase 2b dose-ranging trial in adults (LP0133-1273), a one-sided significance level at 2.5% and a sample size of 92 subjects will provide at least 80% power for detecting a treatment difference in the primary endpoint assuming an IGA-CHE TS response at Week 16 of 40.2% for delgocitinib cream 20 mg/g and 10.5% for cream vehicle.

When the response rates from LP0133-1401 and LP0133-1402 are included in the sample size calculation, this will result in a power which is lower than first anticipated.

The power obtained when using the Bayesian approach on a sample size of 92 subjects is explained in Section [14.3.17](#).

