#### 14.3.17 Description of the Bayesian analyses and design characteristics

The design characteristics is based on 92 randomised subjects (69 in the delgocitinib cream 20 mg/g group and 23 in the cream vehicle group).

For each endpoint, the choice of the between-trial heterogeneity parameter ( $\tau$ ) and the weight on the non-informative part of the prior is described. In addition, the degree of borrowing is described by the ESS and finally, the influence of the type I error and power investigated.

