## **5 Statistical analysis**

### **5.1 General principles**

All frequentist significance tests will be one-sided using the 2.5% significance level. Operationally, the one-sided (superiority) hypotheses will be evaluated by deriving the two-sided p value; the null hypothesis will be rejected if the p value is smaller than 5% and if the point estimate is in favor of the alternative hypothesis.

All confidence intervals will be presented with 95% degree of confidence, unless otherwise specified.

An observed-cases approach will be used for tabulations of data by visit (that is, involving only those subjects who attended each specific visit).

Categorical data will be summarised using the number and percentage of subjects in each category and treatment group. Continuous data will be summarised using the mean, median, SD, 1st quartile, 3rd quartile, minimum, and maximum values.

Baseline measurements will be defined as the latest available observation at or prior to the date of randomization. Subjects without a baseline measurement for a given efficacy score will be excluded from the corresponding analysis.

In case of randomization in wrong stratum with respect to baseline IGA-CHE score, the statistical analyses will use the baseline IGA-CHE score confirmed by the investigator in the eCRF. This is due to the fact that the disease severity according to baseline IGA-CHE score is considered to be a strong prognostic factor for the treatment effect.

Simulation seed used for MI will be 1331426 for both types of imputation (MI based on MAR and MI based on Bernoulli distribution).

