#### **5.5.1.5 Additional analyses for the primary endpoint using the primary estimand and the sensitivity analysis of the primary estimand, Frequentist approach**

To be able to compare the results from LP0133-1426 with the analyses performed in LP0133-1401 and LP0133-1402 two additional analyses will be performed for the primary endpoint using the primary estimand.

In the primary endpoint additional analysis, missing data for subjects who do not experience an IE prior to Week 16 will be imputed as non-response (see Panel 8). The difference in response rates between the two treatment groups will be analysed using the CMH test stratified by baseline IGA-CHE score. The difference in response rates with 95% CI will be calculated by the Mantel-Haenszel method stratified by baseline IGA-CHE score.

THIS DOCUMENT CONTAINS CONFIDENTIAL INFORMATION AND MUST NOT BE COPIED OR MADE AVAILABLE TO ANY THIRD PARTY WITHOUT THE PRIOR WRITTEN CONSENT OF THE LEO PHARMA GROUP

In the sensitivity analysis of primary endpoint additional analysis, missing data for subjects who do not experience an IE prior to Week 16 will be imputed based on a Bernoulli distribution as described in section [5.5.1.3](#).

For each of the 100 complete datasets, the difference in response rates will be analysed by the Mantel-Haenszel method stratified by baseline IGA-CHE score. The results of the analyses will be combined using Rubin's rule to provide the estimated treatment difference and associated standard error, and the 95% CI for the treatment difference will be calculated.

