#### **5.5.1.6 Binary endpoint analyses using the primary estimand, Frequentist approach**

The remaining binary endpoints will be analysed in a similar manner as the primary endpoint (that is including treatment group and baseline IGA-CHE score as factors), see section [5.5.1.2](#).

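### The frequentist risk-difference test and 95% CI, on their natural large-sample reading, do not hold their stated level with about two expected vehicle responders (supportive analysis; should fix)

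*SAP*

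**What the plan says.** SAP 5.1 sets the level: "All frequentist significance tests will be one-sided using the 2.5% significance level". In practice this means a two-sided p-value below 5% with the point estimate favouring delgocitinib.

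SAP 5.5.1.2 states the null hypothesis that the risk difference is zero or less, and adds: "The hypothesis will be tested for delgocitinib cream 20 mg/g vs. cream vehicle based on the primary analysis for the primary estimand". The model is logistic, with treatment and baseline IGA-CHE as factors. On the interval it says: "The logistic regression model will be used to estimate the risk difference and associated 95% confidence interval based on the standardised estimator", with the variance taken from a second cited paper. Protocol 14.3.6 gives the same analysis without the second citation.

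SAP 5.5.1.6 carries the method over: "The remaining binary endpoints will be analysed in a similar manner as the primary endpoint".

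SAP 5.5.1.5 adds a second analysis of the primary endpoint, for comparison with the adult trials: "The difference in response rates between the two treatment groups will be analysed using the CMH test stratified by baseline IGA-CHE score", with a Mantel-Haenszel interval.

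Neither document says what to do if an arm has no responders. The SAP's small-cell provisions (Panel 6 and the augmented likelihood in the Appendix 2 SAS code) serve only the imputation step. SAP 2.1 keeps the frequentist analyses out of the testing hierarchy.

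**The concern.** At the adult vehicle rate, 23 vehicle subjects give about two expected responders. A normal approximation with variances estimated separately in each arm is unreliable there, and the failure is one-sided. When no vehicle subject responds, the logistic fit is separated: the treatment coefficient has no finite estimate, the fitted vehicle risk goes to zero, and so does its estimated variance. The standard error then reflects the active arm alone, and a small active response is enough for significance.

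What is at stake is the reading of the results. The confirmatory Bayesian analysis borrows from adults. The frequentist analysis shows what the adolescent data say without borrowing, and it carries a stated 2.5% test and a stated 95% interval. If these are anti-conservative in delgocitinib's favour, they overstate the support from the trial's own data. The result also depends on an unstated programming choice: whether a separated fit is reported as a valid test or as not estimable.

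**Working it through.** **Inputs from the documents**
- Sample size, Protocol 14.1: "92 subjects will be randomised 3:1 to delgocitinib cream 20 mg/g or cream vehicle". Arms, Protocol 14.3.17: "69 in the delgocitinib cream 20 mg/g group and 23 in the cream vehicle group".
- Adult phase 3 averages for IGA-CHE TS, Protocol Panel 21: vehicle 8.4% (trial values 9.9% and 6.9%), delgocitinib 24.3%.
- Planning rates, Protocol 14.1: 40.2% and 10.5%. Vehicle rate for HESD ≥4, Protocol Panel 39: 21.6%.
- Under the composite estimand missing data count as non-response, so for the primary endpoint the denominators stay at 69 and 23.

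**Assumptions**
- The interval is estimate ± 1.96 SE.
- For the adjusted simulation, 30% of subjects are severe at baseline (the documents give no figure).
- The 21.6% row below uses 69/23, although the HESD endpoints are restricted to subjects with baseline ≥4 and would have fewer.

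**The plan's own figure first.** Protocol 14.1 states at least 80% power for 40.2% against 10.5%. Mean rate = (69×0.402 + 23×0.105)/92 = 0.328. Pooled SE = √[0.328×0.672×(1/69 + 1/23)] = 0.113. Unpooled SE = √[0.402×0.598/69 + 0.105×0.895/23] = 0.0870. Power = Φ[(0.297 − 1.96×0.113)/0.0870] = 80.7%, so the figure reproduces with a pooled-variance test. The fully unpooled formula gives Φ(0.297/0.0870 − 1.96) = 92.7%.

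**Expected vehicle responders.** 23 × 0.084 = 1.93. P(no vehicle responder) = 0.916^23 = 13.3%.

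**Exact size and coverage.** All 70 × 24 outcome tables are enumerated with binomial probabilities. A table rejects if d − 1.96·SE > 0, with d = x₁/69 − x₀/23 and SE² = p̂₁(1−p̂₁)/69 + p̂₀(1−p̂₀)/23.

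| Common rate | Rejects (nominal 2.5%) | of which no vehicle responder | Coverage under no effect | Pooled score test rejects |
|---|---|---|---|---|
| 6.9% | 13.8% | 13.7 points | 85.6% | 0.1% |
| 8.4% | 11.5% | 11.2 points | 87.7% | 0.4% |
| 9.9% | 9.2% | 8.4 points | 89.9% | 0.7% |
| 10.5% | 8.5% | 7.3 points | 90.6% | 0.9% |
| 21.6% | 5.0% | 0.4 points | 93.2% | 2.1% |

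Under the adult effect (24.3% against 8.4%) Wald coverage is 93.6%.

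**The adjusted analysis as planned.** 40,000 simulated trials per scenario of the logistic model with treatment and severity, standardised risk difference, and three forms of variance (delta method, delta method plus covariate sampling, influence-function sandwich). At 8.4% all three give 11.6% rejection and 87.5% coverage. If severity is prognostic (10.0% moderate, 4.7% severe) the results are 11.7% and 87.3%. Adjustment does not change the picture.

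**One table.** Take 4/69 against 0/23. d = 5.8%, SE = √(0.0580×0.9420/69) = 2.81%, z = 2.06, and the 95% CI is 0.3% to 11.3%, so the rule declares superiority. The one-sided Fisher p-value is (69·68·67·66)/(92·91·90·89) = 0.31. With no vehicle responder, a pooled score test would need 11/69.

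**Score interval for comparison.** The Miettinen-Nurminen interval covers 96.3% at 8.4% and 95.0% at 21.6%.

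**Cost under the adult effect.** Wald rejects 56.0% of the time and the pooled score test 37.3%. They disagree in 18.7% of trials.

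**The case against.** **The analysis is not confirmatory.** This stands. Only the Bayesian analyses enter the hierarchy (SAP 2.1). A reader might infer that the trial's success decision is exposed to an 11.5% error rate; the documents do not support that. The point concerns a supportive p-value and interval.

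**It is not the only look at adolescent data without borrowing.** This also stands. The CMH analysis (SAP 5.5.1.5), the Bernoulli sensitivity analysis (5.5.1.3) and the treatment-policy analyses (5.6.1) use adolescent data alone, and the Bayesian sensitivity grid (5.5.1.9) includes a weight of 1 on the non-informative component. SAP 5.5.1.2 is nonetheless the designated primary frequentist analysis, and SAP 5.5.1.5 is labelled additional.

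**The problem is only separation.** Largely true at 8.4%: if separated fits were treated as not estimable, rejection would fall to about 0.3%. It is not true at higher rates. At 21.6%, tables with at least one vehicle responder supply about 4.7 of the 5.0 points, so a zero-responder rule alone would not restore 2.5% there.

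**The Wald form is inferred.** Correct, since the cited variance paper was not available. But no alternative is named, and the imputed versions pool an estimate and standard error by Rubin's rule, which fits that reading.

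**A broad remedy would be disproportionate.** One might suppress the interval whenever an arm has fewer than five responders. At a vehicle rate of 8.4% that would trigger in about 96% of trials. Nor does a score interval supply a standard error for Rubin's rule. Both points limit the fix.

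**Conclusion.** The concern holds for a supportive analysis: should fix. On the natural reading, the stated one-sided 2.5% level and 95% confidence are not delivered. At a common rate of 8.4% the test rejects about 11.5% of the time and the interval covers about 88%. Over the adult and planning vehicle rates for the primary endpoint (6.9% to 10.5%) rejection runs from 13.8% down to 8.5%, and coverage from 85.6% to 90.6%.

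Two stronger readings should be resisted. The 88% is coverage under no effect, not a general property: under the adult effect it is 93.6%. And the 11.5% does not carry over to every binary endpoint: at 21.6% the rejection rate is 5.0%, twice nominal but far from 11.5%.

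The conclusion rests on the inferred Wald form, on arms of 69 and 23, and on separated fits being reported as ordinary results. The assumed 30% severe share affects only the simulation, which agrees with the exact calculation.

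**What to change.** **SAP 5.5.1.2 and 5.5.1.6 (no multiple imputation).** Take the p-value from the CMH test stratified by baseline IGA-CHE, already specified for the primary endpoint in SAP 5.5.1.5, and extend it to the other binary endpoints. Take the risk-difference CI from a stratified Miettinen-Nurminen score method. Keep the standardised logistic risk difference as the point estimate.

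**SAP 5.5.1.3 and 5.6.1.2 (multiple imputation).** Keep the logistic model and Rubin's rule, but state that the model-based CI and p-value are not reported when an arm has no responders, and whether that is judged on the observed or the completed data. These analyses concern only IGA-CHE TS at Week 16. In the exact unadjusted calculation, leaving out tables with no vehicle responder brings rejection to 0.3% at 8.4% and 1.2% at 10.5%.

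**Cost.** SAP wording and modest programming, settled before unblinding. Intervals widen, and the chance of nominal significance at the adult rates falls from about 56% to about 37%. The replacement test is conservative at low rates (the pooled score test rejects 0.4% at 8.4%). Both costs fall on a supportive analysis.
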